High Dose Conditioning With Ifosfamide, Carboplatin, and Etoposide With Autologous Stem Cell Transplantation for Patients With Recurrent Nasopharyngeal Carcinoma

NCT02137096

03/23/2017

HIGH DOSE CONDITIONING WITH IFOSFAMIDE, CARBOPLATIN AND ETOPOSIDE WITH AUTOLOGOUS STEM CELL TRANSPLANTATION FOR PATIENTS WITH RECURRENT NASOPHARYNGEAL CARCINOMA

Investigator(s):

**[name]
[name]
[name]**

1. ABSTRACT / PURPOSE:

Nasopharyngeal carcinoma (NPC) is a rare disease in children and adolescents in the United States. There is no current standard treatment for recurrent disease. Treatment is individualized based on previous treatment (usually combined modality radiation and chemotherapy), sites of disease recurrence, and the patient's overall health status and anticipated tolerance of additional chemotherapy and radiotherapy. NPC is a highly chemosensitive disease, however, maintaining long-term remission is challenging. The role of consolidation with high dose chemotherapy has been investigated in number of pilot studies and shown to be tolerated. In this study, based on prior experience, the combination of high dose ifosfamide, carboplatin and etoposide followed by autologous stem cell rescue will be investigated as a consolidation therapy for locally advanced and metastatic NPC to increase disease remission rate and long term survival.

2. BACKGROUND:

Nasopharyngeal carcinoma (NPC) is a rare tumor in children accounting for approximately 1% of all childhood tumors, it also accounts for 20 – 50% of all primary nasopharyngeal tumors in this age group^{1,2}. It arises from the surface epithelial cells of the nasopharynx and has been associated with Epstein-Barr virus (EBV) infection². Most patients with childhood NPC have undifferentiated histology (WHO type III) and present with locoregionally advanced disease². Pediatric and adolescent patients are treated based on adult regimens with radiotherapy as the principal mode of treatment³. The addition of chemotherapy has been shown to improve survival in patients with locally advanced NPC⁴. Despite standard combined modality therapy, 20 – 30% of patients with NPC will present with recurrent or metastatic disease⁴. Most recurrences occur within the first two years of diagnosis and repeat radiation therapy is often not an option. Various combinations of chemotherapy have been tried in adults and in children with varying results, but overall response and survival have remained dismal.

The use of high dose chemotherapy followed by autologous peripheral blood stem cell (PBSC) transplantation in recurrent NPC has shown promise when compared with standard chemotherapy. Airoldi and colleagues⁵ reported long-term results of high dose chemotherapy as late intensification with autologous PBSC support in 6 patients. After conventional chemotherapy, there was 1 CR (16%), 3 PR (50%), and 2 NC (34%). After high dose chemotherapy, 4 patients achieved CR (66%), 1 PR (17%), and 1 MR (17%). Toxicity was manageable. After a median follow-up of 30 months (range, 14-50), two

patients were alive without disease (34%), one was alive with bone disease (16%), and three (50%) died of disease at 16, 18, and 24 months⁵.

Chen T-Y et al also reported that high dose chemotherapy followed by autologous stem cell transplantation is feasible with acceptable toxicity and can convert partial remission into complete remission⁶.

3. SPECIFIC AIMS:

- 3.1.** To evaluate the response rates for patients undergoing high dose conditioning using Etoposide, Carboplatin and Ifosfamide followed by autologous stem cell transplantation for the treatment of recurrent NPC in children, adolescents, and young adults.
- 3.2.** To evaluate the toxicities associated with undergoing high dose conditioning using Etoposide, Carboplatin and Ifosfamide followed by autologous stem cell transplantation for the treatment of recurrent NPC in children, adolescents, and young adults.

4. RESEARCH PLAN:

4.1. Good Clinical Practice

This study will be conducted in accordance with Good Clinical Practice (GCP), as defined by the International Conference on Harmonisation (ICH) and in accordance with the ethical principles underlying European Union Directive 2001/20/EC and the United States Code of Federal Regulations, Title 21, Part 50 (21CRF50).

The study will be conducted in compliance with the protocol. The protocol, any amendments and the subject informed consent will receive Institutional Review Board/Independent Ethics Committee (IRB/IEC) approval/favorable opinion before initiation of the study.

All potential serious breaches must be reported to University of Florida IRB-01. A serious breach is a breach of the conditions and principles of GCP in connection with the study or the protocol, which is likely to affect, to a significant degree, the safety or physical or mental integrity of the subjects of the study or the scientific value of the study.

Study personnel involved in conducting this study will be qualified by education, training, and experience to perform their respective tasks. This study will not use the services of study personnel where sanctions have been evoked or where there has been scientific misconduct or fraud (eg. loss of medical licensure, debarment). Systems with procedures that ensure the quality of every aspect of the study will be implemented.

4.2. Institutional Review Board/Independent Ethics Committee

Investigators must ensure that subjects (or, in those situations where consent cannot be given by subjects, the legally acceptable representative) are clearly and fully informed about the purpose, potential risks, and other critical issues regarding clinical studies in which they volunteer to participate. Freely given

written informed consent must be obtained from every subject (or, in those situations where consent cannot be given by subjects, the legally acceptable representative) before clinical study participation including informed consent for any screening procedures conducted to establish subject eligibility for the study.

The rights, safety, and well being of the study subjects are the most important considerations and should prevail over interests of science and society.

Subjects unable to give their written consent (eg. children less than 18 years of age, stroke patients, or those with severe dementia) may be enrolled in the study only with the consent of a legally acceptable representative. The subject must also be informed about the nature of the study to the extent compatible with the subjects' understanding, and should they become capable, they must personally sign and date the consent form as soon as possible. The explicit wish of a subject unable to give his or her consent, who is capable of forming an opinion and assessing this information to refuse participation in, or to be withdrawn from, the clinical study at any time should be considered by the investigator.

5. INVESTIGATIONAL PLAN

5.1. Study Design

This is a Pilot study evaluating the role of high dose conditioning with Ifosfamide, Carboplatin, and Etoposide with autologous stem cell transplantation for children, adolescents and young adults with recurrent nasopharyngeal carcinoma.

5.2. Number of Patients Planned

A total of 10 patients are planned to be included in this study.

5.3. Duration of Treatment

The subjects will be on treatment for approximately 3 months which includes the pre-treatment evaluations, the conditioning treatment, and 6-8 weeks of post treatment supportive care.

5.4. Duration of Follow-Up

The subjects will begin follow-up care and the time of initial discharge after transplant and continue for up to 5 years from date of stem cell transplant or until death or patient withdrawal.

5.5. Study Population

5.5.1. Inclusion Criteria

- 5.5.1.1.** Pathologically confirmed nasopharyngeal carcinoma at original diagnosis.
- 5.5.1.2.** Imaging and/or tissue diagnosis of second or greater recurrent or progressive nasopharyngeal carcinoma
- 5.5.1.3.** Documentation of previous treatment including conventional chemotherapy and/or radiation therapy as clinically appropriate.
- 5.5.1.4.** Ages 2 to 30 years of age.
- 5.5.1.5.** Negative serum pregnancy test if applicable.
- 5.5.1.6.** Subjects must agree to use contraception if they are of childbearing age.

5.5.1.7. Prior to initiation of high dose conditioning patient must have completed leukapheresis and stem cell preservation in accordance with institutional standards, with a minimum collection of $4 \times 10^6/\text{kg}$ CD34+ cells desired. Separate institutional informed consent forms will be used.

5.5.1.8. Prior to initiation of high dose conditioning patients must have calculated creatinine clearance of greater than 60 mL/minute, serum creatinine of less than 120 mg/DL, total bilirubin less than 2 mg/dL and AST must be less than twice the upper limit of normal.

5.5.1.9. Hematopoietic recovery prior to initiation of high dose conditioning would include ANC of greater than $1 \times 10^9/\text{L}$, and platelets greater than $100,000 \times 10^9/\text{L}$; or at the discretion of the attending physician based upon clinical situation.

5.5.1.10. Patient and/or parent or legal guardian to sign informed consent form.

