5.5.2. Exclusion Criteria

5.5.2.1. Patient deemed unsuitable for autologous transplantation due to comorbidities or intractable psychosocial issues.

5.5.2.2. Failure to give written informed consent.

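### Two pre-conditioning entry limits are wrong as printed: no patient can reach the platelet limit, and the serum creatinine limit can never exclude anyone who meets the clearance limit

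*Combined protocol and SAP*

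**What the plan says.** Both limits stand in the inclusion criteria of the combined protocol and SAP and apply before high-dose conditioning starts.

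- **5.5.1.8 (organ function).** Patients must have "calculated creatinine clearance of greater than 60 mL/minute", "serum creatinine of less than 120 mg/DL", and "total bilirubin less than 2 mg/dL and AST must be less than twice the upper limit of normal". The criterion is mandatory and contains no discretion clause.
- **5.5.1.9 (blood count recovery).** Recovery is described as an ANC above 1 × 10^9/L and "platelets greater than $100,000 \times 10^9/\text{L", followed by the alternative "or at the discretion of the attending physician based upon clinical situation".

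The age range in 5.5.1.4 is 2 to 30 years. No formula for calculated clearance is named, and no other section restates or corrects either limit.

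**The concern.** In 5.5.1.9 the ANC and platelet limits share one unit. The ANC figure is of ordinary size in that unit, while the platelet figure looks like a per-microlitre count attached to a per-litre unit. In 5.5.1.8 the bilirubin limit shows mg/dL used sensibly, while a creatinine of 120 in that unit is far outside anything a patient with adequate clearance could have.

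These are entry limits for a marrow-suppressing regimen that can damage the kidney. The treatment table gives ifosfamide 2.5 g/m²/day and carboplatin 300 mg/m²/day, each for four days. Both are dosed by body surface, so renal function does not enter the starting dose. Section 5.5.6 lists kidney damage as a risk, for ifosfamide with possible dialysis. Section 16.1 requires the study to be run as the approved protocol describes. A monitor working from the text could not tell a patient who met the platelet threshold from one admitted on discretion, and the separate creatinine requirement would never be a reason to stop.

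**Working it through.** **Inputs from the documents:** platelets above 100,000 × 10^9/L; ANC above 1 × 10^9/L; creatinine below 120 mg/dL; clearance above 60 mL/minute; age 2 to 30 years. **Assumptions:** the clearance formulas, body sizes, a platelet volume of 7–10 fL, and 1 mg/dL creatinine = 88.42 µmol/L.

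**Platelets**

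1. 100,000 × 10^9/L = 10^14/L. Divided by 10^6 microlitres per litre, this is 10^8 per microlitre.
2. The usual form, 100 × 10^9/L, is 10^5 per microlitre. Ratio: 10^8 / 10^5 = 1,000.
3. At 7–10 fL per platelet, 10^14 platelets per litre would occupy 0.7–1.0 L of each litre of blood. No patient can meet the limit.
4. Unit check on the neighbouring limit: ANC 1 × 10^9/L = 1,000 per microlitre, which is plausible.

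**Creatinine in adults, Cockcroft-Gault assumed**

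Clearance = (140 − age) × kg × (0.85 if female) / (72 × creatinine). The highest creatinine compatible with clearance 60 is (140 − age) × kg × (0.85 if female) / (72 × 60).

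| Patient | Calculation | Creatinine cap (mg/dL) | 120 / cap |
|---|---|---|---|
| Woman, 30 y, 45 kg | 110 × 45 × 0.85 / 4,320 | 0.97 | 123 |
| Man, 30 y, 70 kg | 110 × 70 / 4,320 | 1.78 | 67 |
| Man, 18 y, 90 kg | 122 × 90 / 4,320 | 2.54 | 47 |
| Man, 18 y, 200 kg | 122 × 200 / 4,320 | 5.65 | 21 |

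In reverse, an 18-year-old man with creatinine 120 mg/dL would need to weigh 60 × 72 × 120 / 122 = 4,249 kg to have a clearance of 60.

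**Creatinine in younger patients, Schwartz assumed**

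Cap = k × height in cm / 60, with k between 0.413 and 0.7.

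- 85 cm, k = 0.413: 0.59 mg/dL.
- 180 cm, k = 0.413: 1.24 mg/dL.
- 200 cm, k = 0.7: 2.33 mg/dL, and 120 / 2.33 = 51.

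Bedside Schwartz (k = 0.413) returns mL/min per 1.73 m², whereas the protocol states mL/minute. Converting multiplies the cap by body surface / 1.73. This lowers it for small children and raises it for large patients. Reaching 120 from 2.33 would take a surface of about 51 × 1.73 = 88 m², so the mismatch does not alter the result.

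**What a working limit would do**

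The candidates are 1.2 mg/dL and 120 µmol/L, which is 120 / 88.42 = 1.36 mg/dL. By Cockcroft-Gault, a 30-year-old, 70 kg man at 1.2 mg/dL has a clearance of 110 × 70 / (72 × 1.2) = 89 mL/minute; at 1.36 mg/dL it is 79. With creatinine from 1.2 to 1.78 mg/dL (clearance 89 down to 60), he passes as printed and would fail a limit of below 1.2 mg/dL.

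**The case against.** The strongest reply is that little changes in practice. A clinician would probably read the platelet digits as 100,000 per microlitre. The discretion clause is there by design and would survive the correction. Renal entry is still governed by the mandatory clearance limit. It is backed by a baseline clearance or GFR (section 8), renal monitoring with carboplatin adjustment (5.5.4.4), discontinuation for laboratory abnormalities (5.5.3.3), and exclusion of a "Patient deemed unsuitable for autologous transplantation due to comorbidities or intractable psychosocial issues". The documents do not show that a separate creatinine cap would make a patient with clearance of 60–89 mL/minute safer. All of this stands, and it limits the consequence. It does not make either printed limit usable.

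A second reply is that the creatinine value may have lost a decimal point when the PDF was read. That cannot be excluded. Other decimals survive in the same text (2.5 g/m² in the treatment table, 0.25 in the body-weight formula), so loss is not shown either. The creatinine half is therefore less certain than the platelet half, where digits, exponent and unit are all legible.

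A third reply is that the size of the gap depends on the body sizes chosen: the ratio is 47 at 90 kg and 21 at 200 kg. That is correct, but the limit stays inert across the whole range.

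**Conclusion.** Both limits are wrong as printed, subject to a source check for creatinine. The platelet limit is 1,000 times the likely intended value and cannot be met. The creatinine limit is at least 20 times above any value compatible with clearance above 60 mL/minute, under Cockcroft-Gault at 18–30 years and 45–200 kg, or Schwartz up to 200 cm with k up to 0.7. The effect falls on eligibility checking and on one secondary renal check. No endpoint or analysis changes, nor does the sample size of 10.

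Three stronger readings are tempting, and the documents do not support them.

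- **Nobody can be enrolled.** The discretion clause keeps entry open.
- **Patients with failing kidneys can enter unchecked.** The clearance limit is mandatory and sits in the same sentence.
- **A corrected creatinine limit would add nothing for children, so the check is lost in adults only.** This depends on formula and height. A limit of 1.2 mg/dL would already bind for a 180 cm adolescent with k = 0.413 (cap 1.24), and with k = 0.55 above 1.2 × 60 / 0.55 = 131 cm.

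**What to change.** 1. In 5.5.1.9, print platelets as more than 100 × 10^9/L (100,000 per microlitre). The discretion clause can stay.
2. In 5.5.1.8, check the creatinine value in the source PDF. If 120 mg/dL is really printed there, have the sponsor confirm the intended limit and print it with its unit. Neither 1.2 mg/dL nor 120 µmol/L is in the documents, so the choice should not be made for the sponsor.
3. Bring the eligibility form, including any eligibility entry in the ONCORE database, into line.

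The cost is two corrected values and, under section 16.1, an amendment needing IRB approval before use. The downside is that a working creatinine limit may exclude a few patients who pass on clearance, such as the 70 kg man above. In a study of 10 patients sized on availability (15.1), the sponsor should weigh that when choosing the value.

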5.5.2. Exclusion Criteria

5.5.2.1. Patient deemed unsuitable for autologous transplantation due to comorbidities or intractable psychosocial issues.

5.5.2.2. Failure to give written informed consent.

5.5.2.3. Pregnancy

5.5.2.4. Breast-feeding women

5.5.3. Discontinuation of Subjects from Treatment

5.5.3.1. Withdrawal of informed consent (subject's decision to withdraw for any reason)

5.5.3.2. Progressive disease at any time

5.5.3.3. Any clinical adverse event (AE), laboratory abnormality, or intercurrent illness which, in the opinion of the investigator, indicates that continued participation in the study is not the best interest of the subject.

5.5.3.4. Pregnancy

5.5.4. Treatment Plan

5.5.4.1. Stem Cell collection and cryopreservation of peripheral blood stem cells

5.5.4.1.1. The patient will undergo a collection of adequate numbers of hematopoietic stem cells. Stem cell harvesting may be done after priming with a cytokine (G-CSF, GM-CSF or other factors used singly or in combination according to institutional preference) or they may be collected following the salvage chemotherapy during the rebound phase with cytokine support. Chemotherapy in combination with growth factors is also allowed.

5.5.4.1.2. Stem cells should be collected no longer than six weeks after completion of last cycle of salvage chemotherapy. The patient will undergo leukapheresis according to standard institutional procedures to collect a minimum of $4 \times 10^6/\text{kg}$ CD34+ cells desired. Separate institutional informed consent forms will be used.

5.5.4.1.3. The collected cells must be cryopreserved according to accepted methods using DMSO alone or DMSO/HES. The stem cells should not be purged or CD34 selected. The collected stem cells will be reinfused after conditioning chemotherapy.

5.5.4.1.4. Patients who fail to collect adequate CD34 cells will be excluded from the study.

5.5.4.1.5. Stem cells will be thawed and infused according to standard institutional practices on Day 0.

5.5.4.1.6. Patient may receive premedication with diphenhydramine, mannitol, hydrocortisone and acetaminophen per institutional protocol.

5.5.4.2. All patients transplanted per the PEDIATRIC BMT SERVICE will have chemotherapy dosed on actual body weight. If the patient's weight is more than 130% of their ideal body weight, then calculate the doses of chemotherapy according to the adjusted ideal body weight using the following formula:

Adjusted ideal body weight = ideal body weight + [(total body weight-ideal body weight) x 0.25].

5.5.4.2. Dose modifications may occur as clinically indicated, at the discretion of the treating physician.

5.5.4.3. Mesna shall be started prior to initiation of Ifosfamide administration per institutional standard. Other measures of uroprotection, such as hydration and furosemide shall be carried out per institutional standard and at the discretion of the treating physician.

5.5.4.4. Renal function shall be monitored as per institutional standard and Carboplatin dose adjusted if clinically indicated.

| DAYS BEFORE TRANSPLANT | | | | | | |
|--|---------|-------|-------|-------|---------|-------|
| Treatment | Day - 5 | Day-4 | Day-3 | Day-2 | Day - 1 | Day 0 |
| Ifosfamide (2.5 g/m ² /day) IV over 17 hours for four days | X | X | X | X | | |
| Carboplatin (300 mg/m ² /day) IV over 3 hours for four days | X | X | X | X | | |
| Etoposide (300mg/m ² /day) IV over 3 hours for four days | X | X | X | X | | |
| Stem Cell Infusion (Minimum 48 of hours from last dose). | | | | | | X |

5.5.5. Supportive Care

- 5.5.5.1.** Prophylaxis with antiemetics for immediate and delayed nausea and vomiting shall be administered as per current supportive care guidelines.
- 5.5.5.2.** Subjects will have a multilumen indwelling venous catheter placed prior to initiation of therapy.
- 5.5.5.3.** Antibacterial, antiviral and antifungal prophylaxis/treatment will be administered in accordance with current supportive care guidelines.
- 5.5.5.4.** Blood component support will be administered in accordance with current supportive care guidelines.
- 5.5.5.5.** Growth factor support will be administered in accordance with the current supportive care guidelines.

5.5.6. Possible Risks

- 5.5.6.1.** Aggressive supportive care improves outcome. This study will follow the institutional supportive care guidelines for high-dose chemotherapy and stem cell transplant.
- 5.5.6.2.** The possible risks of this treatment include those associated with high-dose chemotherapy and autologous stem cell transplantation including:

1. Pancytopenia requiring transfusion support
2. Bacterial infection
3. Fungal infection
4. Nausea, vomiting
5. Loss of appetite
6. Mucositis
7. Alopecia
8. Allergic reactions to the chemotherapy agents or supportive care agents
9. Liver damage
10. Kidney damage
11. Hemorrhagic cystitis
12. Sinusoidal obstruction syndrome (SOS) of the liver
13. Engraftment syndrome
14. DMSO adverse effects during stem cell infusion

5.5.6.3. Drug specific risks are listed below:

Possible Side Effects of Carboplatin and Etoposide (Table Version Date: October 8, 2013)

COMMON, SOME MAY BE SERIOUS

In 100 people receiving Carboplatin, Etoposide, more than 20 and up to 100 may have:

- Hair loss
- Vomiting, nausea, diarrhea, loss of appetite
- Infection, especially when white blood cell count is low

COMMON, SOME MAY BE SERIOUS

In 100 people receiving Carboplatin, Etoposide, more than 20 and up to 100 may have:

- Anemia which may require blood transfusions
- Bruising, bleeding
- Belly pain
- Sores in mouth which may cause difficulty swallowing
- Tiredness
- Fever, chills

OCCASIONAL, SOME MAY BE SERIOUS

In 100 people receiving Carboplatin, Etoposide, from 4 to 20 may have:

- Constipation
- Numbness and tingling in fingers and toes
- Allergic reaction which may cause rash, low blood pressure, wheezing, shortness of breath, swelling of the face or throat
- Heart failure or heart attack which may cause chest pain, shortness of breath, swelling of ankles, and tiredness
- Severe skin rash with blisters and peeling which can involve inside of mouth and other parts of the body
- Liver damage which may cause yellowing of eyes and skin, swelling

RARE, AND SERIOUS

In 100 people receiving Carboplatin, Etoposide, 3 or fewer may have:

- Changes in vision
- Changes in taste
- Damage to organs which may cause hearing and balance problems
- Cancer of bone marrow (leukemia) caused by chemotherapy

Possible Side Effects of Filgrastim (Table Version Date: October 24, 2013)**COMMON, SOME MAY BE SERIOUS**

In 100 people receiving Filgrastim, more than 20 and up to 100 may have:

- Nausea, vomiting
- Pain in bone

OCCASIONAL, SOME MAY BE SERIOUS

In 100 people receiving Filgrastim, from 4 to 20 may have:

- Anemia which may cause tiredness, or may require transfusion
- Damage to the lungs which may cause shortness of breath
- Internal bleeding which may cause coughing up blood
- Swelling or tenderness of vessels

RARE, AND SERIOUS

In 100 people receiving Filgrastim, 3 or fewer may have:

RARE, AND SERIOUS

In 100 people receiving Filgrastim, 3 or fewer may have:

- Rupture of the spleen leading to bleeding in the belly

Possible Side Effects of Ifosfamide (Table Version Date: May 28, 2013)**COMMON, SOME MAY BE SERIOUS**

In 100 people receiving Ifosfamide, more than 20 and up to 100 may have:

- Anemia which may require transfusion
- Nausea, vomiting
- Infection, especially when white blood cell count is low
- Blood in urine
- Hair loss

OCCASIONAL, SOME MAY BE SERIOUS

In 100 people receiving Ifosfamide, from 4 to 20 may have:

- Abnormal heartbeat
- Bruising, bleeding
- Kidney damage which may cause swelling, may require dialysis
- Fluid around lungs
- Confusion, sleepiness, disorientation
- Sterility

RARE, AND SERIOUS

In 100 people receiving Ifosfamide, 3 or fewer may have:

- Damage to the heart or heart failure which may cause tiredness, shortness of breath, or swelling of ankles

Possible Side Effects of Mesna (Table Version Date: May 28, 2013)**COMMON, SOME MAY BE SERIOUS**

In 100 people receiving Mesna, more than 20 and up to 100 may have:

- Nausea, vomiting
- Tiredness, headache
- Pain in arms, legs
- Unpleasant taste

OCCASIONAL, SOME MAY BE SERIOUS

In 100 people receiving Mesna, from 4 to 20 may have:

- Low blood pressure which may cause feeling faint

RARE, AND SERIOUS

In 100 people receiving Mesna, 3 or fewer may have:

- None

Possible Side Effects related to blood stem cell harvest and infusion

COMMON, SOME MAY BE SERIOUS

In 100 people receiving Ifosfamide, more than 20 and up to 100 may have:

- Nausea and vomiting
- Unpleasant taste and smell of agent used to preserve stem cells when frozen
- Headache
- Fever
- Discolored urine
- Tingling of the lips
- Muscle cramping

OCCASIONAL, SOME MAY BE SERIOUS

In 100 people receiving Ifosfamide, from 4 to 20 may have:

- Seizures (rare)
- Blood loss
- Infection
- Skin rash, hives
- Flushing (redness and warmth of the skin)
- Dizziness or fainting
- Chills
- Changes in heart rhythm (rare and easily treated)

RARE, AND SERIOUS

In 100 people receiving Ifosfamide, 3 or fewer may have:

- In rare cases, patients have allergic reactions (may be life threatening)
- Increased bleeding or clotting (caused by a drug to prevent clotting of the blood during collection)

